## 7.2.2 Early withdrawal/End of Study

Early withdrawal is defined as a patient who is unable to complete one cycle of pazopanib. The following study activities will be completed at early withdrawal or at the end of treatment:

• Physical exam. ECOG performance status. Radiographic examination and assessment of response. Retinal examination for those with known retinal lesions. Serum chemistry and electrolytes to include: albumin, alkaline phosphatase, BUN, calcium, creatinine, glucose, LDH, phosphorus, total protein, Liver Function Test (total bilirubin, SGOT[AST] and/or SGPT[ALT]), sodium, potassium, carbon dioxide, chloride, and lipase. Hematology to include: CBC with differential and platelet count.

• Record for concomitant medications. Monitor for adverse events.

• Optional blood for correlative studies will be obtained. Approximately 30cc of blood will be collected.

## 7.3 Contingency to continue study for responders

After the initial 24 week treatment period, patients who demonstrate clear response/ and or benefit to therapy will be evaluated on a case-by-case basis and may be continued. The follow up schedule and required procedures for the additional cycles will be the same as done previous cycles.

7.4 Contingency for Surgical Intervention

Protocol 2011-0465 ASeptember 6, 2017 Page 36 of 50

Patients who progress either clinically or radiographically and require an immediate surgical intervention will proceed with the appropriate procedures. No washout period is mandated in light of the fact that bleeding and wound healing has not been documented to be a side effect of pazopanib. If there is clinically relevant neutropenia or thrombocytopenia, or other abnormal laboratory parameters that in the opinion of the surgeon or study physician will have a negative impact on surgical outcome, patients will need these values corrected prior to surgery. If patients have given consent for tissue banking, redundant excised tissue will be harvested at the time of surgery by the surgical pathologist.

If there is evidence of continued benefit in other organ(s) i.e. shrinkage or stabilization which can be attributed to study drug, patient will remain on study and drug will be restarted 2 weeks post-surgery or at a later date if patient requires further postoperative recovery, until a lack of further benefit is demonstrated in those organ(s) on restaging scans.

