The most common adverse events reported for pazopanib monotherapy to date are diarrhea, fatigue, nausea, hypertension, hair color changes (hair depigmentation), anorexia, vomiting, dysgeusia, headache, abdominal pain, rash, aspartate aminotransferase (AST) and alanine aminotransferase (ALT) increases, constipation, cough, and arthralgia. Most of these events were Grade 1 or 2 using the National Cancer Institute-Common Toxicity Criteria of Adverse Events, Version 4.0 (NCI-CTCAE, v4.0). The most frequent Grade 3 or 4 events were hypertension, fatigue, diarrhea, and AST and ALT increases. Less common AEs of note include hand-foot syndrome, mucositis/stomatitis, proteinuria, venous thrombotic events, and bleeding. Intestinal perforations and arterial thromboses were uncommon. The most common serious adverse events (SAEs), derived from all pazopanib studies that include studies where pazopanib was administered in combination with chemotherapy, are diarrhea, abdominal pain, vomiting, dyspnoea, hypertension (including one report of hypertensive crisis), pyrexia, anaemia, dehydration, fatigue, pneumonia, pleural effusion, neutropenia, pulmonary embolism, increase in ALT and nausea. Two cases of Torsades de Pointes have been reported in the pazopanib clinical program; however, whether or not there is a causal relationship to pazopanib remains unclear. A number of these events are known class effects of VEGF inhibitors. Therefore, this protocol is designed to closely monitor and provide clear management guidelines for these events based on the clinical experience with pazopanib to date.

2.3 Clinical and Preclinical Studies Assessing Response to Sunitinib in VHL, and Assessment of Endothelial Receptors in Renal Tumor and Hemangioblastoma Endothelium

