#### 4.2.2 Permitted Medications – Use with Caution

#### Specific recommendations regarding anticoagulants:

Results from drug-drug interaction studies conducted in subjects with cancer suggest that pazopanib has no effect on the metabolism of S-warfarin. Hemorrhagic events, however, have been reported in clinical studies with pazopanib; therefore, pazopanib should be used with caution in subjects with increased risk of severe bleeding or who are receiving concomitant anticoagulant therapy (e.g., warfarin or its derivatives, low molecular weight heparin, unfractionated heparin). Subjects taking concomitant anticoagulant therapy should be monitored regularly for changes in relevant coagulation parameters as clinically indicated, as well as for any clinical bleeding episodes.

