## Table 5. Dose Modification Algorithms for Potential Treatment-Related Adverse Events

# Proprietary Information of MD Anderson Protocol 2011-0465

Protocol 2011-0465 ASeptember 6, 2017 Page 24 of 50

AE Terms & Descriptions	Dose Modification Algorithms
Grade 1	For hemoptysis, interrupt pazopanib to discuss whether further treatment with pazopanib is appropriate.
	For other Grade I hemorrhage/bleeding events, continue pazopanib at the current dose; monitor as clinically indicated.
Grade 2	Step 1. If pulmonary or GI bleed (other than hemorrhoidal bleeding), discontinue pazopanib and continue follow-up per protocol. Otherwise, interrupt pazopanib until the AE resolved to ≤ Grade 1.
	Step 2. Restart pazopanib; consider reducing dose and monitor as clinically indicated.
Grade 3 or 4, or	Discontinue pazopanib and continue with follow-up per protocol.
Recurrent $\geq$ Grade 2 event after dose interruption/reduction.	
Venous Thrombosis (DVT, PE)	·
Grade 2	Continue pazopanib at the current dose; monitor as clinically indicated
Grade 3	Step 1. Interrupt pazopanib.
	Step 2. Initiate and monitor anticoagulation as clinically indicated.
	Step 3. Resume pazopanib at reduced dose only if all of the following criteria are met:
	• The subject must have been treated with anticoagulant at the desired level of anticoagulation for at least one week.
	• No Grade 3 or 4 or clinically significant Grade 2, hemorrhagic events have occurred while on anticoagulation treatment.
	Subject should be monitored as clinically indicated during anticoagulation treatment and after resuming study treatment. When treating with warfarin, international normalized ratio (INR) should be monitored within three to five days after any change in pazopanib dosing (eg, re-initiating, escalating/de-escalating, or discontinuing pazopanib), and then at least weekly until the INR is stable. The dose of warfarin (or its derivatives) may need to be adjusted to maintain the desired level of anticoagulation
Grade 4 and/or PE	Discontinue pazopanib and continue follow-up per protocol.
Arterial Thrombosis/Ischemia	
Any Grade	Discontinue pazopanib and continue follow-up per protocol.

Protocol 2011-0465 ASeptember 6, 2017 Page 25 of 50

AE Terms & Descriptions	Dose Modification Algorithms			
Thrombocytopenia: Investigate and document underlying cause				
Grade 1 or 2	Continue pazopanib with current dose; monitor as clinically indicated.			

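### Section 7.4 waives washout before immediate surgery on the ground that bleeding is not a documented effect of pazopanib, but the same protocol documents it

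*Combined protocol and SAP*

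**What the plan says.** Section 7.4 of the combined protocol and SAP applies to patients who progress, clinically or on imaging, and "require an immediate surgical intervention will proceed with the appropriate procedures". It mandates no washout, and the reason it gives is that "bleeding and wound healing has not been documented to be a side effect of pazopanib". It then asks that a low neutrophil or platelet count that matters clinically be corrected before surgery. The same requirement extends to "other abnormal laboratory parameters that in the opinion of the surgeon or study physician will have a negative impact on surgical outcome". If other organs still benefit, the drug restarts 2 weeks after surgery, or later if recovery takes longer.

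Elsewhere the protocol says this about bleeding:

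- Section 2.2, adverse event profile: "Less common AEs of note include hand-foot syndrome, mucositis/stomatitis, proteinuria, venous thrombotic events, and bleeding". The same paragraph ends: "Therefore, this protocol is designed to closely monitor and provide clear management guidelines for these events".
- Section 4.2.2, on anticoagulants: "Hemorrhagic events, however, have been reported in clinical studies with pazopanib; therefore, pazopanib should be used with caution". That caution covers subjects at increased risk of severe bleeding as well as those on anticoagulants.
- Section 6.1, Table 5, titled "Dose Modification Algorithms for Potential Treatment-Related Adverse Events", sets bleeding rules by grade. At Grade 2, for example: "If pulmonary or GI bleed (other than hemorrhoidal bleeding), discontinue pazopanib and continue follow-up per protocol".

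**The concern.** The sentence in 7.4 is the reason attached to an operative rule, and 7.4 is the only section that tells a clinician what to do when a patient on study drug goes to surgery. A surgeon or covering physician who consults that section alone would read that bleeding is not a known problem with this drug. The other sections tell the same reader the opposite.

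What is at stake is perioperative judgement in patients who may be operated on in the brain, spine, kidney or pancreas. Section 7.4 asks for abnormal laboratory values to be corrected. It asks nobody to consider drug-related bleeding or how recently the last dose was taken.

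**Working it through.** The plan gives no figure on this point, so the check is a comparison of text, plus one small calculation on whether a washout would be feasible.

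**1. Is bleeding documented in the protocol?**

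| Place | What it says about bleeding | Bearing on 7.4 |
|---|---|---|
| 2.2 | A less common adverse event of note, among events the protocol undertakes to monitor and manage | Contradicts it |
| 4.2.2 | Hemorrhagic events seen in pazopanib studies, with a caution on use of the drug as a result | Contradicts it |
| Table 5 | Grade 1 hemoptysis: interrupt. Grade 2 pulmonary or non-hemorrhoidal GI bleed: discontinue. Other Grade 2: interrupt. Grade 3 or 4, or recurrence at Grade 2 or above: discontinue | Inconsistent with it: bleeding is handled as potentially treatment-related |
| 3.2, items 2 and 10 | Excludes GI conditions that raise bleeding risk, active bleeding and bleeding diathesis | Consistent with treating bleeding as a risk |

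No section supports the statement in 7.4 on bleeding.

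**2. Is the wound-healing half contradicted?** No. No section lists impaired healing as an effect of pazopanib. Exclusion 9 bars recent major surgery and non-healing wounds at entry, which is a precaution and not a report of harm.

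**3. Does the no-washout rule depend on the faulty reason?** No. Section 4.2.2 gives a mean half-life of 30.9 hours. Take five half-lives as the washout, the multiple that sections 3.1 and 3.2 use for prior drugs (an assumption here). Then 5 × 30.9 = 154.5 hours, and 154.5 / 24 = 6.4 days. A wait of that length does not fit surgery that is needed immediately, so urgency is enough to justify the rule. The same half-life means that drug is still present when a patient is operated on soon after a dose, which is why time since last dose is worth asking about.

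**4. Does the laboratory sentence close the gap?** Only in part. Its wording is broad enough to include coagulation. However, note b of the study calendar (7.5) schedules PT and PTT at screening only, so no routine on-treatment coagulation result would prompt the question. A drug-related bleeding tendency need not appear as an abnormal laboratory value (a clinical assumption that the documents do not address).

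**5. How many patients?** Section 7.4 applies only to those who progress and also need immediate surgery. The documents give neither the expected progression rate nor the share needing surgery, and no perioperative bleeding rate. Neither the exposure nor any excess of bleeding can be computed.

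**The case against.** The strongest case on the other side has four parts.

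- **An adverse event is not a proven side effect.** Sections 2.2 and 4.2.2 report events and do not assert causality for each. That is correct and softens the contradiction. It does not remove it: 7.4 says bleeding has not been documented as an effect, while 4.2.2 draws a drug caution from it and Table 5 stops the drug for it.
- **The rule is unaffected.** A washout makes little sense before immediate surgery, so the fault lies in a reason and no effect on conduct has been shown. This stands, and it limits the severity.
- **Safeguards exist.** Platelets and other laboratory values are corrected before surgery, the caution in 4.2.2 is not confined to anticoagulated patients, and restart can be delayed. These reduce the practical effect but leave the wrong statement in the section a surgeon would consult.
- **Few patients are exposed.** Criterion 4 in section 3.1 requires that patients not be at immediate risk of intervention for any lesion, and CNS lesions must be asymptomatic. This stands too. The repeated interventions described in 2.1 are lifetime history, and the secondary objective on surgery concerns a rate over time. Neither shows that immediate surgery on drug will be common.

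A reader might also try to count patients from section 12.1: 40 × 0.20 = 8 progressions, and 0.8 to 4.0 operations if 10% to 50% of these need immediate surgery. The documents do not support that count. The 20% is a stopping threshold and not a forecast, the share is invented, and clinical progression under 7.4 need not match the monitored progression event.

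**Conclusion.** The bleeding rationale in section 7.4 is wrong on the protocol's own text: two sections contradict it and Table 5 is inconsistent with it. This is an internal inconsistency at an operative decision point, and it rests on no numerical assumption. The number of patients affected cannot be estimated and is probably small. Severity is minor to should-fix: the rule survives, but a false reassurance about safety should not remain as its basis.

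Three stronger conclusions might be inferred, and the documents support none of them. They do not show that a washout is required, since urgency is a sufficient reason to omit it. They do not show that pazopanib impairs wound healing. They do not show that the 2-week restart is wrong: exclusion 13 uses 14 days after surgery and exclusion 9 uses 28 days after major surgery, so the entry criteria do not settle the interval.

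**What to change.** In section 7.4, replace the sentence on washout with:

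*Because surgery is immediate, no washout is mandated. Bleeding has been reported with pazopanib; the surgeon and study physician should take this risk, including time since last dose, into account when preparing the patient for surgery.*

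Leave the laboratory-correction and 2-week restart text as they are. If the clinical team wants to keep the statement on wound healing, it can stand as a separate sentence.

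The cost is one sentence in an amendment and a brief added consideration before an operation. Sample size, stopping boundaries, analysis, dose rules and restart timing do not change. The text asks for preparation and not for delay, so it does not conflict with the urgency of the surgery.

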#### 7.5 Study Calendar

Baseline evaluations are to be conducted within 2 weeks prior to study entry. Scans must be done within 8 weeks of signing the informed consent. In the event that the patient's condition is deteriorating, laboratory evaluations should be repeated within 48 hours prior to initiation of the next cycle of therapy. Cycle 1 physical examination will only have to be repeated in > 7 days from screening.

		Cycle 1	Cycle 2	Cycle 3	Cycle 4	Cycle 5	Cycle 6	Additional Cycles	
	Baseline	Wk 1-4	Wk 5-8	Wk 9-12	Wk 13-16	Wk 17-20	Wk 21-24		Early Withdrawal/Post- Treatment Evaluation d
Pazopanib		Х	Х	Х	Х	Х	Х	Х	
Informed Consent	Х								
History and Physical 	Xj	Х			Х			X m	Х
Concomitant Medications	Х	Х			Х		Х	Х	Х
Performance Status	Х	Х			Х			X m	Х
CBC w/diff, plts	Х	Х	Х	Х	Х	Х	Х	Х	Х
Serum Chemistry b	X k	Х	Х	Х	Х	Х	Х	Х	Х
Protocol 2011-0465 ASeptember 6, 2017 Page 37 of 50

UPRC	Х								
EKG	Х								
Liver Function Tests i	Х	Х	Х	Х	Х	Х	Х	Х	Х
B-HCG	Xc								
Optional Blood for Correlative Studies g	Х			X			Х	Х	Xf
Radiographic and Retinal Examination e,h	Х				Х		Х	Х	Х
Adverse Event Monitoring	X	←					→	Х	Х

a: Pazopanib Dose as assigned; route/schedule.

b: Albumin, alkaline phosphatase, BUN, calcium, creatinine, glucose, LDH, phosphorus, total protein, sodium, potassium, carbon dioxide, chloride, lipase. Note: Add PT and PTT testing at screening only.

c: Serum pregnancy test (women of childbearing potential).

d: Off-study evaluation may take place within 5-7 months after the last dose of study drug.

e. If high-quality baseline measurement is available from an outside institution, this will be considered acceptable. For individuals who do not have retinal lesions, no further retinal evaluations will be necessary for study purposes. If retinal lesions are present, retinal exams must take place every 12 weeks (+/- 7 days)

f. A single sample (approximately 10 cc) at treatment discontinuation (only if related to disease progression).

g. Optional blood also drawn at time of dose reduction or modification

h. Follow-up radiographic scans will take place at the end of cycles 3 and 6, and every 12 weeks thereafter (+/- 7 days).

i. Liver function tests (LFTs) are defined as total bilirubin, SGPT (ALT) and SGOT (AST). For the first eight weeks of study, LFTs will be drawn EVERY TWO WEEKS and every four weeks thereafter.

j. Concurrent non-VHL disease and medical therapy must be documented. All prior anti-VHL treatment must be recorded in proper detail. Any residual toxicity from prior therapies should be recorded by using the grading schema in NCI Common Toxicity Criteria v4.0.

k. Those with known pheochromocytoma will have serum and urinary evaluation.

1. Day 1 of each Cycle. Height (baseline only), weight, and vital signs will be taken during physical exam.

m. Physician exams, interim history, vital signs and performance status will be done every 12 weeks (±7 days)

#### 8.0 ADVERSE EVENTS AND REPORTING REQUIREMENTS

8.1 Reporting Requirements

8.1.1 Adverse Drug Reaction Reporting

Toxicity will be scored using CTC Version 4.0 for toxicity and adverse event reporting. A copy of the CTC Version 4.0 can be downloaded from the CTEP homepage (http://ctep.info.nih.gov). All appropriate treatment areas have access to a copy of the CTC Version 4.0.

Adverse events will for this protocol will be documented and entered into the case report form according the Recommended Adverse event Recording Guidelines for Phase II protocol.

Protocol 2011-0465 ASeptember 6, 2017 Page 38 of 50

Table 8.					
Recommended Adverse Event Recording Guidelines					
Attribution	Grade 1	Grade 2	Grade 3	Grade 4	Grade 5
Unrelated	Phase I	Phase I	Phase I Phase II	Phase I Phase II Phase III	Phase I Phase II Phase III
Unlikely	Phase I	Phase I	Phase I Phase II	Phase I Phase II Phase III	Phase I Phase II Phase III
Possible	Phase I Phase II	Phase I Phase II Phase III			
Probable	Phase I Phase II	Phase I Phase II Phase III			
Definitive	Phase I Phase II	Phase I Phase II Phase III			

The Investigator or physician designee is responsible for verifying and providing source documentation for all adverse events and assigning the attribution for each event for all subjects enrolled on the trial.

## 8.1.2 Serious Adverse Event Reporting (SAE)

An adverse event or suspected adverse reaction is considered "serious" if, in the view of either the investigator or the sponsor, it results in any of the following outcomes:

- Death
- A life-threatening adverse drug experience any adverse experience that places the patient, in the view of the initial reporter, at immediate risk of death from the adverse experience as it occurred. It does not include an adverse experience that, had it occurred in a more severe form, might have caused death.
- Inpatient hospitalization or prolongation of existing hospitalization
- A persistent or significant incapacity or substantial disruption of the ability to conduct normal life functions.
- A congenital anomaly/birth defect.

Important medical events that may not result in death, be life threatening, or require hospitalization may be considered a serious adverse drug experience when, based upon appropriate medical judgment, they may jeopardize the patient or subject and may require medical or surgical intervention to prevent one of the outcomes listed in this definition. Examples of such medical events include allergic bronchospasm requiring intensive treatment in

Protocol 2011-0465 ASeptember 6, 2017 Page 39 of 50

an emergency room or at home, blood dyscrasias or convulsions that do not result in inpatient hospitalization, or the development of drug dependency or drug abuse (21 CFR 312.32).

- Important medical events as defined above, may also be considered serious adverse events. Any important medical event can and should be reported as an SAE if deemed appropriate by the Principal Investigator.
- All events occurring during the conduct of a protocol and meeting the definition of a SAE must be reported to the IRB in accordance with the timeframes and procedures outlined in "The University of Texas M. D. Anderson Cancer Center Institutional Review Board (IRB) Policy for Investigators on Reporting Unanticipated Adverse Events for Drugs and Devices".
- Serious adverse events will be captured from the time of the first protocol-specific intervention, until 30 days after the last study treatment/intervention, unless the participant withdraws consent. Serious adverse events must be followed until clinical recovery is complete and laboratory tests have returned to baseline, progression of the event has stabilized, or there has been acceptable resolution of the event.
- Additionally, any serious adverse events that occur after the 30 day time period that are related to the study treatment must be reported in accordance with the IRB policy. This may include the development of a secondary malignancy.
- 8.1.3 Reporting to FDA

SAE's will be reported per regulatory (local and federal) guidelines.

It is the responsibility of the PI and the research team to ensure that serious adverse events are reported according to the Code of Federal Regulations, Good Clinical Practices, the protocol guidelines, the sponsor's guidelines, and Institutional Review Board policy.

Investigator Communication with Supporting Companies.

### **Reporting to Novartis**

The investigator must assess and record the relationship of each SAE to each specific study drug (if there is more than one study drug) and report only SAEs arising in subjects exposed to the Novartis Study Drug(s). Complete the SAE Report in English. Send the completed and signed form by fax, within 24 hours of first becoming aware of the event, to Novartis. . You must report safety data to Novartis by fax to:

- US CPO DS&E [contact]
  - Should the designated SAE Fax# be non-functional please send SAEs to the designated SAE mailbox:

Protocol 2011-0465 ASeptember 6, 2017 Page 40 of 50

## [contact]

- Please include Novartis SAE report coversheet for any SAE report (Attached)
  - Novartis Study Code (CPZP034XUS34T) must be on the SAE coversheet

